### **7.1.1      Temporary Discontinuation from Study Intervention**

Participants who have an elective major surgery during the study may be treated with other FVIII, according to local practice at the discretion of investigators. Participants will resume their treatment assignment of Jivi as per this protocol after surgical recovery.

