# **7. Discontinuation of Study Intervention and Participant Discontinuation/Withdrawal**

## **7.1 Discontinuation of Study Intervention**

- Inhibitor development

Any inhibitor development ( $\geq 0.6$  BU/mL, confirmed) is considered a SAE.

Discontinuation of study intervention due to a high titer inhibitor development (titer  $> 5$  NBU/mL) should be considered by the investigator if the investigator believes that it is in the best interest of the participant and/or if bypassing agents are needed to treat bleeds. Participants who discontinue study intervention due to inhibitor development cannot continue in the study and will be withdrawn.

- Planned major surgery during the study

If the participant has a planned elective surgery during the study, the investigator and sponsor will determine if the participant can continue in the study and if any change in participant management is needed.

See the SoA for data to be collected at the time of intervention discontinuation and for any further evaluations that need to be completed.

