### Counting of bleeds:

- 'All bleeds' will include all bleeds, regardless of treated or untreated (untreated bleeds will only be available from study 19764)
- A bleed will be counted as treated bleed if either the flag variable from the diary indicates that the bleed was treated or there is a matching infusion for this bleed (regardless of product used).

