### ABR:

$$\text{Annualized number of bleeds} = \frac{\# \text{ of bleeds} * 365.25 * 24 * 60}{\text{period}}$$

*Period* is defined as the number of minutes calculated from the date and time of the beginning of the evaluation period and the date and time of the end of the evaluation period.

Evaluation periods for study 19764:

- Main efficacy period: Time from injection at visit 3 to end of treatment
- Complete study: Time from first injection at visit 2 to end of treatment

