### Treatment administration:

Documented infusions with other FVIII products or with a dose of 0 IU will be excluded. Infusions with a missing dose will be counted for number of infusions and exposure days but will be excluded from other treatment administration analyses.

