### **6.4 Safety**

All safety analyses will be performed on the SAF. MedDRA codes of studies 13024 and 15912 will be updated by the MedDRA version used for study 19764. An AE will be considered treatment-emergent if it starts after first injection and not later than 7 days after last injection of Jivi.

Overview tables displaying all AEs, all pre-treatment AEs and all treatment emergent adverse events (TEAEs) will be created. All subsequent tables will be presented by MedDRA preferred term (PT) and system organ class (SOC). Serious AEs, TEAEs, serious TEAEs, drug-related TEAEs, serious drug-related TEAEs, TEAEs of special interest, TEAEs causing discontinuation of study drug, TEAEs by maximum intensity, drug-related TEAEs by maximum intensity, non-serious TEAEs, and AEs leading to death will be presented.

Overview tables, all TEAEs, serious TEAEs, drug-related TEAEs and serious drug-related TEAEs will be displayed by subgroups.

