**BAY 94-9027 / 19764**

Page: 15 of 17

Subject listings will be provided for all participants from study 19764 with at least one positive FVIII inhibitor measurement/BAY 94-9027 antibody measurement/PEG antibody measurement/PEG IgM antibody measurement showing all FVIII inhibitor/BAY 94-9027 antibody/PEG antibody/PEG IgM antibody (respectively) laboratory measurements as well as FVIII recovery results of these participants, including the number of ED before the measurement dates and the date of the last injection before measurement dates.

All measurement results for inhibitors including repeated measurements in case of positive results will be displayed by time point and presented in subject listings.

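### Time and bleeds on another FVIII around elective major surgery enter the Jivi ABR, and the SAP has no rule to separate that interval

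*Protocol*

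**What the plan says.** Protocol 7.1.1 covers temporary discontinuation. Participants with an "elective major surgery during the study may be treated with other FVIII, according to local practice", and "Participants will resume their treatment assignment of Jivi as per this protocol after surgical recovery". It sets no limit on the length of the interval. Under Protocol 7.1, when elective surgery is planned during the study, "the investigator and sponsor will determine if the participant can continue in the study". A major surgery already planned at entry is an exclusion (Protocol 5.2).

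The SAP rules that meet this interval are:

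- **ABR (SAP 4.5).** The number of bleeds is divided by elapsed minutes. One period is defined as "Complete study: Time from first injection at visit 2 to end of treatment"; the main efficacy period starts instead at the Visit 3 injection. End of treatment is 7 days after the latest infusion, or end of study if earlier, so a gap in mid-study does not close the period.
- **Bleeds counted (SAP 4.5).** The all-bleeds category takes every bleed, treated or not, and sets no condition on the product in use at the time.
- **Exposure (SAP 4.5, Treatment administration).** "Documented infusions with other FVIII products or with a dose of 0 IU will be excluded". The sentence that follows applies the section to exposure days (ED). The ED definition in SAP 6.1 does not name a product.
- **TEAEs (SAP 6.4).** An event is treatment-emergent if it "starts after first injection and not later than 7 days after last injection of Jivi".
- **Inhibitor and antibody listing (SAP 6.4).** It shows all measurements and recovery results, "including the number of ED before the measurement dates" and the date of the last injection. Other FVIII products are not among the named items.

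**The concern.** The protocol foresees non-Jivi time inside follow-up, but no SAP rule deals with it. The same weeks are left out of treatment administration yet count in full as time at risk for the ABR, so the ABR of an affected participant is a blend of two products. If the interval is free of bleeds, it dilutes the Jivi rate. If perioperative bleeds occur, it inflates the rate. Because use of the other product follows local practice, the blending can differ between sites.

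Protocol 9.3 says that safety participants are analyzed by the intervention they actually received, and no SAP rule carries that idea into this interval. The SAP already accepts the principle elsewhere: its pooled efficacy analysis (SAP 6.2) drops the on-demand part of participants who later switched to prophylaxis.

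On the safety side the issue is what the reader can see. Protocol 9.4.2 says that the inhibitor listing should bring out clinical factors that may be associated with an inhibitor. Recent exposure to another FVIII is such a factor, and the listing as specified would not show it. If no rule is set in advance, the handling will be chosen in an open-label study after a case is known.

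**Working it through.** **Inputs from the documents.** Start with every-5-day dosing for 8 to 10 weeks, then twice weekly, every 5 days or every 7 days until 100 ED of Jivi (Protocol 4.1). The main ABR period starts at Visit 3 (SAP 4.5).

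**Assumptions.** The documents do not give the gap length (taken as 2, 4 or 8 weeks) or the number affected (taken as 1 to 3 of 25). The gap falls after Visit 3, the participant still reaches 100 ED of Jivi, and ED from treating bleeds are ignored.

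**Check of the plan's own figure.** Ten weeks of every-5-day dosing gives 70/5 = 14 ED, leaving 86.

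- Twice weekly: 86 × 3.5 = 301 days; total 371 days = 1.02 years
- Every 5 days: 86 × 5 = 430 days; total 500 days = 1.37 years
- Every 7 days: 86 × 7 = 602 days; total 672 days = 1.84 years

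This agrees with the 1 to 2 years stated in Protocol 4.1.

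**Effect on one participant, no bleeds in the gap.** With Jivi time T and gap g, the planned ABR is T/(T + g) of the on-Jivi ABR, so the understatement is g/(T + g).

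| Regimen after Visit 3 | T (days) | g = 14 | g = 28 | g = 56 |
|---|---|---|---|---|
| Twice weekly | 301 | 14/315 = 4.4% | 28/329 = 8.5% | 56/357 = 15.7% |
| Every 5 days | 430 | 14/444 = 3.2% | 28/458 = 6.1% | 56/486 = 11.5% |
| Every 7 days | 602 | 14/616 = 2.3% | 28/630 = 4.4% | 56/658 = 8.5% |

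Over the complete study period the effect is slightly smaller. For 4 and 8 weeks it is 28/399 = 7.0% and 56/427 = 13.1% on twice weekly, and 28/700 = 4.0% and 56/728 = 7.7% on every 7 days.

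**Bleeds in the gap.** Take 3 bleeds on Jivi, twice-weekly dosing and a 4-week gap:

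- Interval removed: 3 × 365.25/301 = 3.64 per year
- As planned, no gap bleeds: 3 × 365.25/329 = 3.33
- As planned, one gap bleed: 4 × 365.25/329 = 4.44

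The sign changes once the bleed rate in the gap exceeds the rate on Jivi. One bleed is enough here.

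**Effect on the mean of 25, no gap bleeds, similar ABRs.** The largest individual shift gives 15.7%/25 = 0.6% with one participant affected and 3 × 15.7%/25 = 1.9% with three. A mean by regimen moves more because its group is smaller; those group sizes are not known.

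**Inhibitors.** This part follows from silence in the SAP. SAP 6.4 counts confirmed inhibitors and has no rule on intervening products. Each case carries weight: 0/25 has an exact 95% interval of 0 to 13.7%, and 1/25 is 4.0% (0.1 to 20.4%).

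**The case against.** Much of the case on the other side stands, and it narrows the point.

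- **Other FVIII use is not hidden.** Protocol 6.5 and 8.1.1 require it to be recorded in the CRF and the diary. SAP 6.1 groups FVIII medications and lists new antihemorrhagics for this study. A confirmed inhibitor is an SAE, and its causality assessment must weigh concomitant therapy and timing (Protocol 10.3.3). A reader might infer that an inhibitor after surgery would be put down to Jivi with no trace of the other product. The documents do not support that: no passage attributes it, and only the inhibitor listing lacks the information.
- **Leaving other-product ED out of the 100-ED target is correct.** Protocol 4.1 and SAP 3 define that target as ED of Jivi. What remains is that the ED definition in SAP 6.1 is product-neutral and should match SAP 4.5.
- **The treated-bleed rule does not decide what enters the ABR.** The words "there is a matching infusion for this bleed (regardless of product used" only define when a bleed is called treated. The point rests on the all-bleeds rule.
- **Counting every AE and inhibitor from first dose is conservative** in a safety study. Nothing in the documents could show that the other product caused an inhibitor, so an inhibitor proportion without such cases should not stand beside the primary result.
- **Protocol 7.1 and 7.1.1 need not conflict.** A reader might see one leaving continuation open and the other assuming it. Section 7.1.1 can be read as covering those who continue.
- **Consistency with the earlier studies.** SAP 4.1 requires data handling in line with studies 13024 and 15912. Their SAPs are not available here, so this has to be checked before the rule changes.

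None of this answers the ABR point. The definition as written mixes non-Jivi time and bleeds into a Jivi rate.

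**Conclusion.** The concern holds for the ABR and follows directly from the written definitions. It holds as a transparency gap for TEAEs and for the inhibitor listing. Under an assumed gap of 4 to 8 weeks without bleeds, an affected participant's main-period ABR is understated by about 8.5 to 15.7% on twice-weekly dosing and 4.4 to 8.5% on every-7-day dosing. Bleeds in the gap can turn this into an overstatement.

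A reader might infer that the study's overall ABR is materially biased or that the primary endpoint is compromised. Neither follows. With 3 of 25 affected and no gap bleeds the mean moves by about 2% or less, the study is descriptive, and the entry exclusion together with case-by-case continuation should keep the number of such participants small. This is an inexpensive improvement to the SAP. It implies no change to clinical management.

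**What to change.** **SAP 4.5, ABR.** Exclude from both numerator and denominator the interval from the first infusion of another FVIII given as temporary replacement to the first resumed Jivi infusion. Report the unbroken-period ABR as a sensitivity analysis. First confirm that this is compatible with the handling already used for studies 13024 and 15912.

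**SAP 6.4.** Keep all TEAEs and all confirmed inhibitors in the main tables. Flag AEs that start in the interval. Add the dates and ED of other FVIII products to the inhibitor and antibody listing.

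**SAP 4.5 and 6.1.** State that the 100-ED count is of Jivi ED only, so that the exclusion rule and the ED definition agree.

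**Cost.** SAP wording and minor programming on data already collected, and slightly less evaluated time for the few participants concerned. The ABR is computed in minutes, while incomplete concomitant-medication dates are imputed (SAP 4.3), so the start of some intervals may be imprecise. The sensitivity analysis shows whether that matters.

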## **7.2      Participant Discontinuation/Withdrawal from the Study**

A participant who withdraws is one who discontinues from a clinical study for any reason. The participant will not suffer any disadvantage as a result.

- A participant may withdraw from the study at any time at his own request without giving reasons, or may be withdrawn at any time at the discretion of the investigator for safety, behavioral, compliance, or administrative reasons..
- At the time of discontinuing from the study, if possible, an early discontinuation/final visit should be conducted, as shown in the SoA. See SoA for data to be collected at the time of study discontinuation and follow-up and for any further evaluations that need to be completed.
- The participant will be permanently discontinued both from the study intervention and from the study at that time.
- If the participant withdraws consent for disclosure of future information, the sponsor may retain and continue to use any data collected before such a withdrawal of consent.
- A participant must be withdrawn from the study if the development of an inhibitory antibody to Jivi that neutralizes activity sufficiently to interfere with effective treatment or requires use of a bypassing agent to treat bleeds.
- A participant must be withdrawn from the study if he fails to comply with scheduled appointments for the study-related evaluations and with EPD data entry to an extent that compromises collection of critical data.
- A participant must be withdrawn from the study if significant concurrent illness or deterioration occurs in the participant's condition, including laboratory values that the investigator deems to be incompatible with the participant's continued safe participation in the study.

### 7.3 Lost to Follow Up

A participant will be considered lost to follow-up if he repeatedly fails to return for scheduled visits and is unable to be contacted by the study site.

The following actions must be taken if a participant fails to return to the clinic for a required study visit:

- The site must attempt to contact the participant and reschedule the missed visit as soon as possible and counsel the participant on the importance of maintaining the assigned visit schedule and ascertain whether or not the participant wishes to and/or should continue in the study.
- Before a participant is deemed lost to follow up, the investigator or designee must make every effort to regain contact with the participant (where possible, 3 telephone calls and, if necessary, a letter to the participant's last known mailing address or local equivalent methods). These contact attempts should be documented in the participant's medical record.
- Should the participant continue to be unreachable, he will be considered lost to follow up.

## 8. Study Assessments and Procedures

- Study procedures and their timing are summarized in the SoA and visit description Section 10.4. Protocol waivers or exemptions are not allowed.
- Immediate safety concerns should be discussed with the sponsor immediately upon occurrence or awareness to determine if the participant should continue or discontinue study intervention.
- Adherence to the study design requirements, including those specified in the SoA, is essential and required for study conduct.
- All screening evaluations must be completed and reviewed to confirm that potential participants meet all eligibility criteria.
- Procedures conducted as part of the participant's routine clinical management (e.g., blood count) and obtained before signing of the ICF may be utilized for screening or baseline purposes provided the procedures met the protocol-specified criteria and were performed within the time frame defined in the SoA.
- If deemed necessary for an individual participant, the investigator or designee, at his/her discretion, may arrange visits in addition to the scheduled study visits. Unscheduled visits will be documented in the eCRF.

## 8.1 Efficacy Assessments

This is a post authorization safety study (PASS). The efficacy endpoints are secondary endpoints for the study and include:

Secondary Endpoints throughout the study

- ABR

Other exploratory endpoints pre-specified throughout the study

- Percentage of participant with 0 spontaneous bleeds during a 6-month treatment
- Total number of exposures
- Consumption: dose/kg per participant/year
- Type, location and severity of bleeds, reason for each injection, and response to treatment of bleeds

Further endpoints are specified in the SAP.

### 8.1.1 Treatment Logs/Bleeding Verification

Treatment logs are commonly used for hemophilia participants for documentation of their home treatment. Home treatment and bleeding information are the key variables for evaluation of efficacy. Study specific treatment logs will be provided in national language. The system for this study will be electronic patient diary (EPD) devices since they are interactive, allow for real time data transmission, record-stamp date and time of fulfillment and facilitate the clarification of data with the site and also the data cleaning process.

Participants will be provided with EPDs for the whole study. At Screening visit, participants will be trained in the use of the device. These logs will be used to collect the treatment data and bleeding episodes by the participants, and the data will be verified for accuracy and completion by the investigator or delegate during regularly scheduled interactions with the participant. Thus, the EPD will be considered the source for these data.

For each self-administered injection of Jivi, information must be recorded on the EPD as follows:

#### Each injection of Jivi:

- a. Date and time
- b. Injection record
- c. Individual vial number (bar code scan from vial label or manual entry) and units administered
- d. Reason for treatment

Prophylaxis

Spontaneous bleed first treatment

Trauma bleed first treatment

Follow-up treatment

Other

Injections of Jivi as part of protocol mandated visits and procedures will be recorded on the respective CRF pages.

All bleeding episodes (regardless if treated or not, or treated at home or under medical supervision) as well as any potential treatment with other hemophilia drugs will be recorded in the EPD:

**Bleeding episode (onset)**

- a. Date and time of onset
- b. Type of bleed (spontaneous, trauma; joint, muscle, skin/mucosal, internal, other)
- c. Location
- d. Intensity (mild, moderate, severe)
- e. Treated [yes/no];
  - if "yes": Date and time
  - Product used: Jivi or other
  - Doses

If Jivi is used for the treatment of a bleeding episode, the response to treatment (excellent, good, moderate, poor, too early to tell) must to be recorded

For guidance to the participant, the following definitions for response to treatment are suggested:

**Excellent:** Abrupt pain relief and/or improvement in signs of bleeding with no additional injection administered

**Good:** Definite pain relief and/or improvement in signs of bleeding, but possibly requiring more than one injection for complete resolution

**Moderate:** Probable or slight improvement, with at least one additional injection for complete resolution

**Poor (or None):** No improvement or condition worsens.

**8.1.2 Incremental Recovery of Jivi**

Blood samples for Jivi trough (predose) and recovery levels (15-30 min post injection) will be collected in all participants. Incremental recovery will be determined by collecting a sample for FVIII level before the scheduled injection, and a second sample collected 15-30 min after end of the injection. The exact sampling times before and after injection and the dose administered will be documented in the CRF. Incremental recovery of Jivi is determined by measuring FVIII activity.

Injections given at study visits will be recorded in the site participant records, which will be the source documents and will be used to enter this information in the CRF.

The samples will be collected as described in detail in the laboratory manual. All samples will be processed in the central laboratory. Plasma concentrations of FVIII will be measured using a validated FVIII activity assay ("chromogenic assay").

Samples for incremental recovery should be collected on days when the next prophylactic injection is scheduled and at least 72 h after the prior injection has been given. The measurements should only be performed when the participant is not actively bleeding.

Recoveries should be performed using the participants assigned treatment dose, rounded to full vial size.

Samples will be collected at Baseline, Visit 3 (Week 8-10), and Last Visit, or in case of suspicion of loss of efficacy (LoE)/hypersensitivity and at additional time points based on the investigator's discretion.

### 8.1.3 Activity Tracker

CCI

## 8.2 Safety Assessments

Planned time points for all safety assessments are provided in the SoA.

The safety endpoints for the study include:

Primary Endpoints throughout the study:

- FVIII inhibitor development by the Nijmegen Bethesda assay. Any positive inhibitor test will be confirmed by testing a second separately drawn sample in a central laboratory

Secondary Endpoints throughout the study:

- TEAE.
- Treatment-emergent anti-drug antibodies (ADA) against Jivi and Anti-PEG antibodies at the same time points as the FVIII inhibitor tests and in case of clinical suspicion of LoE/Hypersensitivity

### 8.2.1 Measurements of Immunogenicity

All participants will be tested for immunogenicity at Screening, Baseline (Day 1), Visit 3, Visit 4, Visit 5, and Last Visit, or in case of suspicion of LoE/hypersensitivity.

### **Antibodies to Jivi and/or PEG (ADA)**

Binding antibodies to Jivi and/or PEG are analyzed in an enzyme-linked immunosorbent assay (ELISA) Type screening ADA assay using Jivi. Positive screened samples will be characterized for specificity of the antibody response against Jivi and/or against PEG and for their neutralizing activity.

### **FVIII inhibitor**

FVIII inhibitor testing will be done according to the Nijmegen modified Bethesda assay. A positive inhibitor test is defined with a threshold of  $\geq 0.6$  BU at the central laboratory.

If an inhibitor is detected as part of scheduled testing, the investigator will be notified. Repeat testing within 2 to 4 weeks of notification should be obtained. Any positive test will be confirmed by a second different sample. Only after confirmation of the positive result, the inhibitor has to be reported as SAE.

